6.3. Method of blinding

Due to the different vaccination schedules between the various study groups the study will be open-label.

The laboratory in charge of the laboratory testing will be blinded to the treatment, and codes will be used to link the subject and study (without any link to the treatment attributed to the subject) to each sample.

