9.1.6.3. Meningitis

For further evaluation of the safety signal of meningitis, all cases of meningitis occurring during the study will be reported as a SAE and additional clinical details of each case will be reported in a specific eCRF screen.

Investigators will be instructed to report cases according to the following case definitions:

- Clinically suspected meningitis:** A child with sudden onset of fever and one of the following signs: neck stiffness, altered consciousness not due to an alternative more probable cause, or other meningeal sign such as bulging fontanelle in children less than one year of age.
- Confirmed meningitis:** A child with clinically suspected meningitis with confirmatory evidence of meningitis from cerebrospinal fluid (CSF) examination.
- Etiology-confirmed meningitis:** A child with confirmed meningitis and evidence from CSF examination of a specific causative agent.

The recommended method for evaluation of meningitis will be through CSF analysis. Lumbar puncture should be performed by qualified medical personnel in subjects when there is an indication for testing. The initial CSF testing to aid in the diagnosis of meningitis including, and not limited to, microscopy and gram staining, differential white cell and red blood cell count, CSF biochemistry, antigen/agglutination tests and culture, amongst others, is to be carried out by the site. For every suspected meningitis case, a CSF sample will be collected and from this approximately 500 µl will be sent to CLS South Africa for CSF polymerase chain reaction (PCR) testing for selected common aetiological pathogens of meningitis (see [APPENDIX D](#) for details of additional tests available at CLS South Africa for the evaluation of meningitis).

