11.2. Secondary endpoints

- **Efficacy:**
 - The occurrence of clinical malaria meeting the primary and secondary case definitions from Day 0 up to Month 50.
 - The occurrence of incident *P. falciparum* infections from Day 0 to Month 50.
 - The prevalence of *P. falciparum* infections defined by positive blood slide at each cross-sectional survey.
- **Immunogenicity: Immune response to the CS and HBs antigens (immunogenicity subset)**
 - *Anti-CS antibody concentrations and seropositivity measured before Dose 1, one month post-Dose 2 (group Fx017-mFxD only), before and one month post-Dose 3, before and one month after Dose 4, before and one month after each yearly dose and at study end (Month 50).*
 - Anti-HBs antibody concentrations and seropositivity measured before Dose 1, one month post-Dose 2 (group Fx017-mFxD only), before and one month post-Dose 3, before and one month after Dose 4, before and one month after each yearly dose and at study end (Month 50).

Amended 14 November 2019

- **Safety**
 - The occurrence of SAEs (all, fatal and related) during the whole study period according to the MedDRA classification.
 - The occurrence of AEs and SAEs leading to withdrawal from further vaccination from Dose 1 (Day 0) up to Month 50, according to the MedDRA classification.
 - The occurrence of severe malaria cases and cerebral malaria cases during the whole study period.
 - The occurrence of pIMDs from Day 0 up to Month 50, according to the MedDRA classification.
 - The occurrence of meningitis from Day 0 up to Month 50, according to the MedDRA classification.
 - The occurrence of seizures within 30 days (day of vaccination and 29 subsequent days) after each dose of study vaccine, according to the MedDRA classification.
 - The occurrence of generalized convulsive seizure within seven days (day of vaccination and six subsequent days) after each dose of study vaccine, according to the Brighton collaboration guidelines [[Bonhoeffer](#), 2004].

- The occurrence of unsolicited AEs within 30 days (day of vaccination and 29 subsequent days) after each dose of study vaccine, according to the MedDRA classification.
- The concentration of biochemistry (ALT, creatinine) and hematology (hemoglobin, WBC, platelets) parameters in the first 50 subjects (25 subjects per site) enrolled in each group (reactogenicity sub-cohort) before Dose 3, seven days post-Dose 3 and 30 days post-Dose 3.
- **Reactogenicity (reactogenicity sub-cohort)**

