The percentage of subjects reporting an AE or SAE leading to withdrawal from further vaccination from Dose 1 (Day 0) until Month 50, classified by the MedDRA preferred term level, will be tabulated with exact 95% CI.

The percentage of subjects reporting severe malaria cases and cerebral malaria cases from Day 0 up to Month 14, Day 0 up to Month 26, Day 0 up to Month 50 and over successive years within the study will be tabulated with exact 95% CI. The percentage of subjects reporting pIMDs from Dose 1 (Day 0) until Month 14, from Day 0 until Month 26 and from Day 0 until Month 50, classified by the MedDRA preferred term level will be tabulated with exact 95% CI.

The percentage of subjects reporting meningitis from Dose 1 (Day 0) until Month 14, from Day 0 until Month 26 and from Day 0 until Month 50, classified by the MedDRA preferred term level will be tabulated with exact 95% CI.

The percentage of subjects reporting seizures occurring within 30 days (day of vaccination and 29 subsequent days) after each dose of study vaccine, classified by the MedDRA preferred term level will be tabulated with exact 95% CI.

For generalized convulsive seizures occurring within seven days following a dose of study vaccine, an analysis will be performed based on the Brighton Collaboration guidelines [Bonhoeffer, 2004]. This includes descriptive tables of the time relationship of seizures to vaccination, the duration of seizures and the level of diagnostic certainty.

Biochemistry (ALT, creatinine) and hematology (hemoglobin, WBC, platelets) values that are outside of the reference ranges (see [Table 29](#)) will be described in the reactogenicity sub-cohort (first 50 subjects enrolled in each group) before Dose 3, seven days post-Dose 3 and 30 days post-Dose 3. Frequency distribution of results by toxicity grades will be tabulated by group.

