The percentage of subjects reporting an SAE (all, fatal, related) from Dose 1 (Day 0) until Month 14, from Day 0 until Month 21, from Day 0 until Month 26, from Day 0 until Month 33 and over the whole study duration (Dose 1 [Day 0] until Month 50), classified by the MedDRA preferred term level, will be tabulated with exact 95% CI.

The percentage of subjects reporting an AE or SAE leading to withdrawal from further vaccination from Dose 1 (Day 0) until Month 50, classified by the MedDRA preferred term level, will be tabulated with exact 95% CI.

The percentage of subjects reporting severe malaria cases and cerebral malaria cases from Day 0 up to Month 14, Day 0 up to Month 21, Day 0 up to Month 26, Day 0 up to Month 33 and Day 0 up to Month 50 and over successive years within the study will be tabulated with exact 95% CI.

The percentage of subjects reporting pIMDs from Day 0 up to Month 14, Day 0 up to Month 21, Day 0 up to Month 26, Day 0 up to Month 33 and Day 0 up to Month 50, classified by the MedDRA preferred term level will be tabulated with exact 95% CI.

The percentage of subjects reporting meningitis from Day 0 up to Month 14, Day 0 up to Month 20, Day 0 up to Month 26, Day 0 up to Month 32 and Day 0 up to Month 50 classified by the MedDRA preferred term level will be tabulated with exact 95% CI.

The percentage of subjects reporting seizures occurring within 30 days (day of vaccination and 29 subsequent days) after each dose of study vaccine, classified by the MedDRA preferred term level will be tabulated with exact 95% CI.

For generalized convulsive seizures occurring within seven days following a dose of study vaccine, an analysis will be performed based on the Brighton Collaboration guidelines [Bonhoeffer, 2004]. This includes descriptive tables of the time relationship of seizures to vaccination, the duration of seizures and the level of diagnostic certainty.

Biochemistry (ALT, creatinine) and hematology (hemoglobin, WBC, platelets) values that are outside of the reference ranges (see protocol section 7.5.2.1) will be described for the reactogenicity sub-cohort (first 50 subjects enrolled in each group) before Dose 3, seven days post-Dose 3 and 30 days post-Dose 3. Frequency distribution of results by toxicity grades will be tabulated by group.

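### Meningitis, a known safety signal, is tabulated only by MedDRA preferred term; a by-group table by the protocol's three certainty levels should be added

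*SAP*

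**What the plan says.** The protocol treats meningitis as an event to be characterised. Its risk table (1.3.1) lists it as an important potential risk, after an imbalance in the phase III study that included cases with and without an identified cause. Section 9.1.6.3 opens: "For further evaluation of the safety signal of meningitis, all cases of meningitis occurring during the study will be reported as a SAE". It then states: "Investigators will be instructed to report cases according to the following case definitions". Three levels follow:

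- **Clinically suspected:** sudden fever plus one clinical sign. No CSF result is needed.
- **Confirmed:** "A child with clinically suspected meningitis with confirmatory evidence of meningitis from cerebrospinal fluid (CSF) examination".
- **Etiology-confirmed:** a confirmed case with a specific agent found in CSF.

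The same section provides a dedicated eCRF screen, and calls for CSF from every suspected case with part of it sent for PCR.

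The endpoint in protocol 11.2 is "The occurrence of meningitis from Day 0 up to Month 50, according to the MedDRA classification"; SAP 5.2 repeats it. Protocol 11.10 plans "The percentage of subjects reporting meningitis from Dose 1 (Day 0) until Month 14, from Day 0 until Month 26 and from Day 0 until" (the last window closes at study end), by preferred term. SAP 7.5.1 plans "The percentage of subjects reporting meningitis from Day 0 up to Month 14, Day 0 up to Month 20" and ends its list of windows with "Day 0 up to Month 32 and Day 0 up to Month 50 classified by the MedDRA preferred term level will be tabulated with exact"; the intervals are at the 95% level. None of these mentions the three levels. SAP Section 4 restates the definitions of severe and cerebral malaria but gives none for meningitis.

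On blinding, protocol 6.3 says: "Due to the different vaccination schedules between the various study groups the study will be open-label".

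**The concern.** The suspected level rests on clinical judgement, made by staff who know the child's group and know that meningitis is a flagged risk. Confirmation in CSF is less exposed to that knowledge. A table that does not separate the levels cannot show whether a difference between groups lies in confirmed disease or in how readily meningitis was suspected.

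A second route needs no conscious bias. It is an inference, not something the documents state. The suspected definition excludes altered consciousness with a more probable alternative cause. The sample-size section (11.4) expects more clinical malaria in Control (0.5 episodes per person-year) than in the standard (0.29) or fractional (0.16) schedules. The same febrile presentation might therefore be put down to malaria more often in Control.

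What is at stake is how clearly the trial can report on a signal it set out to evaluate. Protocol 11.12.1 also lets the IDMC recommend suspending vaccination or ending groups after the interim analyses, so a readable table matters before study end.

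**Working it through.** The documents give no meningitis rate, expected count or margin, so there is no figure of the plan's own to reproduce. The check is first a comparison of passages, then an illustration on assumed inputs.

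**1. Collection against analysis**

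| Item | Meningitis | Generalized convulsive seizures within 7 days |
|---|---|---|
| Graded certainty in the source material | Yes, three levels (protocol 9.1.6.3) | Yes, Brighton guidelines |
| Specific eCRF screen | Yes | Yes |
| Tabulated by certainty (SAP 7.5.1) | No, preferred term only | Yes |

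The SAP's additional safety analyses (7.5.2.1 to 7.5.2.3) cover laboratory grades, concomitant medication and vaccination, and listings of severe and cerebral malaria. None concerns meningitis.

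**2. What differential suspicion could do**

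Assume equal true risk of confirmed meningitis in all arms. Let s be the number of suspected-only cases per confirmed case in Control, and k the relative readiness to suspect in the RTS,S arms. Neither value is in the documents. Then

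ratio of all reported cases = (1 + s × k) / (1 + s), while the ratio of confirmed cases = 1.00.

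- s = 0.5, k = 1.5: 1.75 / 1.5 = 1.17
- s = 1, k = 2: 3 / 2 = 1.50
- s = 2, k = 2: 5 / 3 = 1.67
- s = 3, k = 3: 10 / 4 = 2.50
- k = 1, any s: 1.00

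The plan prints group percentages, not a ratio. The ratio only summarises what a reader comparing two rows would see.

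**3. How much small counts can carry**

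Protocol 5.1 gives 300 children per group, so the RTS,S arms pooled have 4 × 300 = 1200. Exact (Clopper-Pearson) 95% intervals, the SAP's own method, are:

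- 0/300: 0 to 1.22%
- 1/300: 0.01 to 1.84%
- 3/300: 0.21 to 2.89%
- 4/1200: 0.09 to 0.85%

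No between-group test is planned. As a yardstick only, Fisher's exact two-sided p against 0/300 in Control is 0.59 for 4/1200, 0.054 for 16/1200 and 0.021 for 20/1200. If counts are low, a few unconfirmed reports can change the visible pattern. By the same token, confirmed cases alone would seldom settle the question.

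**The case against.** Several points on the other side stand.

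- **No departure by the SAP.** The protocol's own endpoint and analysis section also specify MedDRA classification only. The gap is inherited.
- **The trial's data can still separate the levels.** Investigators report by the three definitions, details go on a specific screen, and every case is an SAE that is updated as information arrives. A reader might infer that the trial cannot tell disease from suspicion. The documents support only that the planned table cannot.
- **Equal counting is not established.** A reader might infer that a suspected case with normal CSF and an etiology-confirmed case count alike. The documents do not say whether the former keeps a meningitis term. Reports are also reviewed and coded, and preferred terms may separate some causes, though nothing maps them to the three levels.
- **Confirmation is not free of the same problem.** Section 9.1.6.3 has lumbar puncture done when indicated and initial CSF testing done at the site. It gives no CSF threshold for confirmation. The blinding of the testing laboratory in protocol 6.3 helps, but the text does not say that it covers site testing.
- **Other outputs may exist.** SAP 11.2 keeps the table and listing contents in a separate file, so a meningitis listing there cannot be excluded.

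The strongest objection concerns the remedy. A reader might infer that CSF-confirmed cases should become the main row. The phase III signal concerned meningitis of any etiology, including cases with none found. For a safety signal, the all-reported count is the more sensitive choice and closest to what was seen before. It should stay.

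None of this supplies a planned analysis by level, or a rule for suspected cases that CSF does not confirm.

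**Conclusion.** The point holds as a cheap and worthwhile improvement. The protocol grades meningitis by certainty in order to evaluate a known signal, and the specified analyses discard that grading while keeping it for convulsive seizures. In an open-label trial, the planned table could not separate a difference in readiness to suspect from a difference in confirmed disease.

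A reader might go further and infer that the planned table is biased against the vaccine. The documents do not support that. They contain no evidence that suspicion differs between arms, and none on its size. The range of 1.17 to 2.50 rests wholly on assumed s and k and on equal true risk; with k = 1 there is no distortion. The conclusion rests on the text of the two documents, and would soften if the separate table contents already include an output by level.

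**What to change.** Keep the planned table of all reported meningitis cases. In SAP 7.5.1, add beside it:

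- a by-group table and a case listing by the three protocol 9.1.6.3 levels;
- the number of suspected cases with CSF obtained, per group;
- the RTS,S arms shown separately and pooled, next to Control;
- a stated rule for counting suspected cases with negative CSF and those with no CSF.

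Do not replace the all-reported count with confirmed cases as the main row. The definitions can be cited from the protocol or restated in SAP Section 4.

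The cost is one table, one listing and one counting rule, with no new study procedure. The case information appears to be collected already; if the eCRF screen has no field for the level, it would have to be derived from the case details and CSF results. The downside is one more table with small counts, and confirmation that depends on CSF having been obtained. The row showing CSF obtained makes that dependence visible.

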1. DOCUMENT HISTORY

Date	Description	Protocol Version
04 SEP 2019	First Version	Amendment 2 Final : 06 APR 2017
24 SEPT 2020	second Version: - update of the follow-up period up to M21 and not M20, up to M33 and not M32 - for the elimination codes: when the same elimination code is given for immunogenicity and efficacy. For some of these elimination codes which are for immunogeniticty Per Protocol (PP) set and efficacy PP set, for the immunogenicity PP, all the doses have to be considered but for efficacy PP set, only the three first doses have to be considered. Therefor for efficacy PP set in these cases, a new elimination code has been given	Amendment 2 Final : 06 APR 2017
01 OCT 2020	Third Version: - for the elimination codes for immunogencity: for the dynamic allocation: o the elimination code 2100 (which is all serological result not available post-vaccination) is eliminated from the list of elimination codes involved in the dynamic allocation o the elimination code 2080 (which is a vaccination out of schedule) goes from visit-specific elimination to elimination of all the visits posterior to the dose affected.	Amendment 2 Final : 06 APR 2017

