9. CONDUCT OF ANALYSES

9.1. Sequence of analyses

All analyses (including interim analyses) will be conducted on data as clean as possible.

- Sequence of analyses and conditional continuation:
 - A first analysis will be performed on data collected up to Month 21 (Visit 25) to evaluate the primary objective (cleaned data) and relevant secondary objectives.
 - A second analysis will be performed on data collected up to Month 33 (Visit 31) to evaluate relevant secondary objectives.
 - A final analysis will be performed at study end (Month 50) on data collected up to Month 50. An integrated study report presenting all results until Month 50 will be produced.
- After the interim analyses, the Independent Data Monitoring Committee (IDMC) will have the possibility to recommend the suspension of further vaccinations and termination of specific study group(s) upon consideration of the study results. In the event that the IDMC recommend the suspension of further vaccinations, the group(s) impacted will be followed up for 12 months after their last study vaccination.

Description	Disclosure Purpose (CTRS=public posting, SR=study report, internal)
Final analysis E1_01	SR, CTRS
Analysis M21 E1_02	SR, CTRS
*Analysis M33 E1 03	CTRS

^{*}The need for a SR will be evaluated at a later time point depending on regulatory need.

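### The cumulative meningitis table in SAP 7.5.1 stops at Months 20 and 32, while the comparable safety tables stop at the interim data cuts of Months 21 and 33

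*SAP*

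**What the plan says.** SAP 7.5.1 gives four outcomes cumulative periods that include interim cut-offs.

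- SAEs are tabulated to Month 14, then "from Day 0 until Month 21, from Day 0 until Month 26, from Day 0 until Month 33", then over the whole study.
- Severe and cerebral malaria use Months 14, 21, 26, 33 and 50.
- For pIMDs the sentence begins "The percentage of subjects reporting pIMDs from Day 0 up to Month 14, Day 0 up to Month 21" and goes on to Months 26, 33 and 50.
- For meningitis the next sentence begins "The percentage of subjects reporting meningitis from Day 0 up to Month 14, Day 0 up to Month 20"; after Month 14 its list in full is "Day 0 up to Month 20, Day 0 up to Month 26, Day 0 up to Month 32 and Day 0 up to Month 50".

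SAP 9.1 takes the first interim analysis on data to Month 21 (Visit 25) and the second on data to Month 33 (Visit 31). The entry for the second version in SAP section 1 describes an "update of the follow-up period up to M21 and not M20, up to M33 and not M32". SAP section 10, on changes from planned analyses, gives no reason for treating meningitis differently.

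Protocol 11.10 lists Months 14, 26 and 50 for meningitis, so the Month 20 and 32 periods are additions made in the SAP. Protocol Table 1 lists meningitis as an important potential risk because of an imbalance in the Phase III trial. Protocol 9.1.6.3 has every case reported as an SAE, with extra clinical detail on its own eCRF screen.

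**The concern.** Meningitis is the only one of the four outcomes whose periods do not match the interim data cuts. The two outdated months are also vaccination visits in some groups: Month 20 is Dose 4 in R012-20 and Fx017-20, and Month 32 is Dose 5 in Fx017-20. In those groups the table closes on the day a dose is given, although about a month of later data is in the database.

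The stake is the coherence of the interim report on a flagged signal. A case arising between Month 20 and Month 21 would be counted in the SAE table to Month 21 but not in the meningitis table beside it. A reader who goes to the dedicated table for the meningitis count would get a lower figure, with nothing in the SAP to explain the difference. SAP 9.1 plans a study report and public posting of the Month 21 analysis, and public posting of the Month 33 analysis.

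**Working it through.** No sample size, power or alpha figure is involved. The check compares the periods and then does schedule arithmetic.

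**Periods in SAP 7.5.1 (months from Day 0)**

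| Outcome | Cut-offs |
|---|---|
| SAEs | 14, 21, 26, 33, 50 |
| Severe and cerebral malaria | 14, 21, 26, 33, 50 |
| pIMDs | 14, 21, 26, 33, 50 |
| Meningitis | 14, 20, 26, 32, 50 |

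**Inputs**

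- Dose months (SAP section 10; protocol Table 2): R012-20 at 0, 1, 2, 20; R012-14 and Fx012-14 at 0, 1, 2, 14, 26, 38; Fx017-20 at 0, 1, 7, 20, 32; Control at 0, 1, 2.
- Planned size: 300 per group, 1500 in all (protocol 5.1).
- Allowed interval from Visit 24 to Visit 25, and from Visit 30 to Visit 31: 21 to 35 days (SAP section 2, visit intervals).

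**Formula.** Follow-up visible after a dose = cut-off month − dose month.

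| Group and dose | Cut at 20 | Cut at 21 | Cut at 32 | Cut at 33 |
|---|---|---|---|---|
| R012-20, Dose 4 (Month 20) | 0 | 1 | 12 | 13 |
| Fx017-20, Dose 4 (Month 20) | 0 | 1 | 12 | 13 |
| R012-14 and Fx012-14, Dose 4 (Month 14) | 6 | 7 | 18 | 19 |
| Fx017-20, Dose 5 (Month 32) | – | – | 0 | 1 |
| R012-14 and Fx012-14, Dose 5 (Month 26) | – | – | 6 | 7 |

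After Dose 3, the Month 20 cut shows 20 − 2 = 18 months in R012-20, R012-14, Fx012-14 and Control, and 20 − 7 = 13 months in Fx017-20.

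**How many group-doses fall to zero.** By Month 20 the five groups have 4 + 4 + 4 + 4 + 3 = 19 group-doses, of which 17 have follow-up above zero. By Month 32 they have 4 + 5 + 5 + 5 + 3 = 22, of which 21 do.

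**Subjects affected, by planned enrolment.** First interim: 2 × 300 = 600 of 1500 (40%), so about 600 person-months of post-dose follow-up are left out. Second interim: 1 × 300 = 300 of 1500 (20%), about 300 person-months. For an individual child the omitted stretch is 21 to 35 days if the visit windows are kept.

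**When the gap closes in the dedicated table.** The Month 26 period gives 26 − 20 = 6 months after the Month 20 dose, but Month 26 lies beyond the first data cut, so this appears only at the second interim. The Month 50 period gives 50 − 32 = 18 months after the Month 32 dose, at the final analysis.

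**The case against.** The strongest reply is that the information is already in the interim outputs. Meningitis must be reported as an SAE. SAP 7.5.1 tabulates SAEs by MedDRA preferred term cumulatively to Months 21 and 33, and also within 30 days of each dose. The second of those tables covers the very window at issue. Nor is a protocol requirement missed, since Months 14, 26 and 50 are all kept. All of this stands, and it limits the point to consistency between tables.

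Three stronger readings are tempting, and the documents do not support them.

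- A reader might infer that the interim meningitis tables show no post-dose follow-up at all. Only Dose 4 in two groups and Dose 5 in one group fall to zero. R012-14 and Fx012-14 keep six months after Dose 4 at Month 20 and six months after Dose 5 at Month 32.
- A reader might infer that the Independent Data Monitoring Committee (IDMC) would not see a case when it considers suspending vaccination. Protocol 6.4.1 gives it periodic safety reports and new information bearing on subject safety, and the SAE tables would carry the case. Its charter is not among the documents, and nothing says it relies on this table.
- A reader might infer that the first month after a dose is a known risk window for meningitis. Protocol Table 1 reports that the Phase III imbalance showed no clustering in time to onset.

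It can also be said that a mismatch with a version history is not in itself an error. That is right. The history is used here only as a sign of intent; the point rests on the differing periods within SAP 7.5.1 and on the data cuts in 9.1.

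What the reply does not explain is why this one table should differ. pIMDs are also reported as SAEs, so their dedicated table is equally duplicated, yet it uses Months 21 and 33.

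**Conclusion.** The inconsistency is real and minor. The dedicated meningitis table omits about one month of available follow-up at each interim. That brings follow-up to zero after the Month 20 dose in R012-20 and Fx017-20 at the first interim, and after the Month 32 dose in Fx017-20 at the second. Elsewhere it shortens follow-up that remains above zero. The consequence is a possible disagreement between the meningitis and SAE tables in the same report, with no loss of cases.

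This assumes that the tables are programmed to the months as written and that subjects attend on schedule. The figures of 600 and 300 are planned enrolment; the numbers actually receiving those doses will differ.

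**What to change.** In the meningitis sentence of SAP 7.5.1, change Month 20 to Month 21 and Month 32 to Month 33, and check that the table shells use the same cut-offs. If the earlier months were intended, state the reason in SAP section 10 and footnote the table so that its counts can be reconciled with the SAE table.

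The cost is two numbers in the SAP. The data already lie within the interim cuts, and the study design, alpha and conduct are unchanged.
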